### 7.8.2 Secondary and Exploratory Immunogenicity Endpoint(s)

The secondary and exploratory immunogenicity endpoints for this trial are listed in Sections 5.2 and 5.3, respectively. Secondary endpoints include seroresponse rates, GMT or BT50 and GMFR for Pan-Ig and HBGA assays at Day 57 (Cohort 1) and Day 140 (Cohort 2). CCI [REDACTED]

However, for summaries and analyses (as applicable) of secondary and exploratory endpoints for a particular assay, all time points will be presented together in the table.

As a reference for summary purposes, secondary and exploratory parameters are listed with all collection time points, separately according to whether continuous or binomial, in the two subsections below.

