### **9.1.6      Immunogenicity Assessments**

Subjects in Cohort 1 in all vaccine arms will undergo blood sampling for serological immunogenicity testing on Day 1 (prior to the first vaccination), Day 29 (prior to the second vaccination), Day 57 (28 days after the second vaccination), and Day 210; Subjects in Cohort 2 will undergo blood sampling for serological testing on Day 1 (prior to the first vaccination), Day 56 (prior to the second vaccination), Day 84 (28 days after the second and 28 days prior to the third vaccination), Day 140 (28 days after the third vaccination), and Day 293. To alleviate the pain associated with blood sampling in this pediatric population, blood collection will be performed by experienced, trained personnel who routinely obtain blood from infants and children, under the supervision of the Principal Investigator after optional application of EMLA cream/patch and using pediatric size needles. All blood samples will be collected in accordance with acceptable laboratory procedures. For serology in all subjects, the volume of blood taken at any single visit is approximately 2 mL. For subjects (without CMI testing), the approximate total volume of blood in the trial is 8 mL for Cohort 1 subjects in Groups 1, 2, 2a, and 3 (4 blood draws) and 10 mL for Cohort 2 subjects in Group 4 (5 blood draws). For those subjects with CMI, a subset of the subjects aged  $\geq$  3 years at selected sites in Groups 1 and 2 only, an additional volume of 3 mL of blood at each of three time points will be drawn immediately prior to and approximately 28 days after each vaccination (Days 1, 29, and 57) for a subtotal of approximately 9 mL. To clarify, for those children aged 3 years and older selected to be in the CMI subset in Groups 1 and 2 only, a total of 17 mL per subject will be obtained for the entire study period. Because subjects in Group 2a will not participate in CMI testing, the total volume of blood for Group 2a subjects is 8 mL. Likewise, the total volume of blood for Group 3 subjects remains at 8 mL. To clarify, for the youngest infants, those in Cohort 2 (Group 4), a total of 10 mL per subject will be obtained for the entire study period. All blood samples will be processed and stored at the trial site according to the Laboratory Guidelines as provided in the Procedures Manual.

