**Placebo Control:**

Saline will be administered as a single control injection (as the final dose) in order to maintain the trial blind for the 1 dose groups in Groups 1, 2, 2a and 3 (Cohort 1) and for the 2 dose group in Group 4 (Cohort 2). Subjects in the 1 dose groups in Cohort 1 receive NoV vaccine on Day 1 and a saline placebo injection on Day 29. Subjects in the 2 dose group in Cohort 2 receive NoV vaccine on Days 1 and 56 and a saline placebo injection on Day 112.

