## **7.8 Immunogenicity Analysis**

### *General Methodology*

The primary population for immunogenicity analyses will be the PPS. Supportive immunogenicity analyses on primary and key secondary endpoints will also be performed using FAS.

Descriptive statistics for the primary, secondary, and exploratory endpoints will be computed for all available assays at all relevant time points and include the following:

- Titer values (eg, GMT, BT50, GMFR): geometric mean, GSD, 95% CIs, minimum, and maximum;
- Other continuous endpoints: mean, SD, median, minimum, and maximum;
- Categorical variable (eg, seroresponse rate): number and percentage of subjects, and 95% CIs in specified categories. The 95% CI of seroresponse rate will be calculated using exact (Clopper-Pearson) method.

Cohorts will be analyzed separately due to different number of doses (1 or 2 in Cohort 1; 2 or 3 in Cohort 2).

Analysis of covariance (ANCOVA) will be conducted for continuous outcome parameters (eg, GMT, GMFR), examining the effect of formulation/dose combination using log-transformed values of the endpoint as the dependent variable and the corresponding log-transformed baseline (pre-vaccination) value as a continuous covariate. The ANCOVA models will include group as a factor for analyses of Cohort 1 with a group by formulation/dose combination interaction term if

appropriate as follows. If the interaction term p-value is  $\leq 0.05$ , the term will remain in the model. If the p-value is  $>0.05$  it will be removed. For Cohort 1, the model will include estimates for treatment (formulation/dose combination) effect within each group, and at the cohort level across groups. A factor for country will be included in all models.

For binomial outcomes the Cochran-Mantel-Haenszel (CMH) method [2] for difference in proportions will be conducted, stratified by group (Cohort 1).

All pairwise comparisons (with the lower level as a reference group) will be presented, without adjustments for multiplicity.

Pre-specified comparisons of interest will be tested. The pre-specified comparisons of interest are the following:

- “A: 15/15, 1 Dose” vs. “A: 15/15, 2 Dose”
- “A: 15/15, 1 Dose” vs. “B: 15/50, 2 Dose”
- “B: 15/50, 1 Dose” vs. “C: 50/50, 1 Dose”
- “B: 15/50, 1 Dose” vs. “B: 15/50, 2 Dose”
- “C: 50/50, 1 Dose” vs. “B: 15/50, 2 Dose”
- “C: 50/50, 1 Dose” vs. “C: 50/50, 2 Dose”
- “C: 50/50, 1 Dose” vs. “D: 50/150, 2 Dose”
- “D: 50/150, 1 Dose” vs. “D: 50/150, 2 Dose”

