#### Secondary and Exploratory Continuous Immunogenicity Endpoints

The secondary and exploratory continuous immunogenicity endpoints are listed below:

- CCI
- 
- 
- 
- 
- 
- 
- 

GMT, BT50 and GMFR will be summarized descriptively, as described in the General Methodology of Section 7.9, for each of the 8 formulation/dose combinations (4 formulation arms; 1 and 2 [or 2 and 3] doses), by group, at each scheduled time point. These summaries will

also be provided at the cohort level, ie, by pooling subjects across the relevant groups. These summaries will be provided for the subjects in the PPS and FAS.

The GMT and BT50 will be calculated as the anti-logarithm of  $\sum(\log \text{transformed titer}/n)$ , ie, as the anti-logarithm transformation of the mean of the log-transformed titer, where n is the number of subjects with titer information. The GSD for GMT and BT50 will be calculated as the anti-logarithm transformation of the standard deviation of the log-transformed titer. The 95% CI will be calculated as the anti-logarithm transformation of the upper and lower limits for a two-sided CI for the mean of the log-transformed titers.

[figure not shown]
GMFR will be calculated as anti-logarithm of  $\sum (\log \text{transformed (post-vaccination titer/ pre-vaccination titer)}/n)$ . The GSD and 95% CIs for GMFR will be calculated similarly to those for GMT and BT50.

GMT, BT50 and GMFR will be analyzed with an ANCOVA model examining the effect of formulation/dose combination using the log-transformed value as the dependent variable and the corresponding log-transformed baseline value as a covariate. The ANCOVA models will include group as a factor for analyses of Cohort 1 with a group by formulation/dose combination interaction term included if appropriate, as follows. If the interaction term p-value is  $\leq 0.05$ , the term will remain in the model. If the p-value is  $>0.05$  it will be removed. For Cohort 1, the model will include estimates for treatment (formulation/dose combination) effect within each group, and at the cohort level across groups. A factor for country will be included. All the applicable pairwise comparisons will be provided with lower levels as the reference groups, with no adjustments for multiplicity. The 14 comparisons of interest listed in the *General Methodology* of Section 7.8 will be tested. The analyses will be based on the PPS.

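### Before the dose regimens diverge (Day 29 in Cohort 1, Days 56 and 84 in Cohort 2), titres should be compared by formulation with the two dose-number arms pooled, not by eight arms

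*SAP*

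**What the plan says.** **Injections.** SAP 4.4 (Placebo Control) states for Cohort 1: "Subjects in the 1 dose groups in Cohort 1 receive NoV vaccine on Day 1 and a saline placebo injection on Day 29". For Cohort 2 it states: "Subjects in the 2 dose group in Cohort 2 receive NoV vaccine on Days 1 and 56 and a saline placebo injection on Day 112". So the dose-number arms first differ at the Day 29 injection in Cohort 1 and at the Day 112 injection in Cohort 2.

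**Blood draws.** Protocol 9.1.6 puts the second Cohort 1 sample at "Day 29 (prior to the second vaccination"). It puts the second and third Cohort 2 samples at "Day 56 (prior to the second vaccination), Day 84 (28 days after the second and 28 days prior to the third vaccination").

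**Summaries.** SAP 7.8.2 (continuous endpoints) summarises GMT, BT50 and GMFR for each of the eight formulation/dose combinations, by group, "at each scheduled time point". Its opening text says of the results for an assay that "all time points will be presented together in the table", with a qualifier that analyses appear where they apply.

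**Comparisons.** The ANCOVA factor is the formulation/dose combination. The SAP adds: "All the applicable pairwise comparisons will be provided with lower levels as the reference groups, with no adjustments for multiplicity". SAP 7.8 (General Methodology) says "Pre-specified comparisons of interest will be tested" and lists 14 pairs, labelled only by 1 and 2 doses. Seroresponse to both antigens together is analysed in the same way as the primary endpoint; single-antigen seroresponse is only summarised. No readable text pools the dose-number arms at any visit.

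**The concern.** At these early visits the dose-number label describes what a child will receive later, not what the child has received. A contrast between two dose-number arms of one formulation therefore estimates a difference that the design sets to zero, and any small p-value would be a chance result that looks like a dose effect. A contrast between formulations that uses one arm of each leaves out half the children who had the same product.

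The early visits bear on the stated aim of selecting a formulation. Day 29 is the only sample 28 days after a single active dose in Cohort 1; by Day 57 the 1-dose arms are 56 days past it. Day 84 is the only sample 28 days after a second active dose in Cohort 2; by Day 140 the 2-dose arms are 84 days past it. What is at stake is precision on those readings, and the risk of reporting two or three different answers to one formulation question.

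**Working it through.** **1. The plan's own arm sizes.** SAP 4.4 gives about 15 per arm in each Cohort 1 group and about 45 in Cohort 2. Check: 120/8 = 15 and 360/8 = 45. Both reproduce.

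**2. What the 14 listed pairs become at Day 29.** Write A1 for formulation A in the 1-dose arm, and so on.

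| Contrast | Listed pairs | Count |
|---|---|---|
| Same formulation | A1–A2, B1–B2, C1–C2, D1–D2 | 4 |
| B v C | B1–C1, C1–B2, B2–C2 | 3 |
| A v B | A1–B2, A2–B2 | 2 |
| C v D | C1–D2, C2–D2 | 2 |
| A v C, A v D, B v D | A2–C2, A2–D2, B2–D2 | 1 each |

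4 + 3 + 2 + 2 + 3 = 14. So 4 tests are null by design and 10 tests address 6 formulation contrasts. The repeated tests share arms: B1–C1 and C1–B2 share C1, and both A v B tests share B2.

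**3. Cohort 2.** The list names no 2-versus-3-dose pair. Eight arms give 8×7/2 = 28 pairwise comparisons. Four are same-formulation pairs. The other 24 cover the same 6 formulation contrasts four times each.

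**4. Chance findings.** The SAP states no alpha; its 95% intervals imply 0.05 two-sided per test, unadjusted. For four null tests, if independent, 1 − 0.95^4 = 18.5% per endpoint and visit. A simulation of the eight-arm ANCOVA (4,000 trials, four groups of 15 per arm, no interaction) gave 18.75%, with 5.1% per test. ANCOVA of log titre and of log fold rise, both with log baseline as covariate, gives the same arm contrasts, so a chance result for GMT repeats for GMFR.

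**5. Precision.** The standard error of a formulation contrast is proportional to sqrt(2/n). Doubling n multiplies it by 1/sqrt(2) = 0.707, so intervals are 29% narrower whatever the SD. In the simulation the ratio of standard errors was 1.4146, against sqrt(2) = 1.4142.

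The documents give no SD. Assume a log10 titre SD of 0.5 (range 0.4 to 0.6). The 95% limits of a GMT ratio are the estimate multiplied and divided by 10^(1.96 × SD × sqrt(2/n)):

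| Setting | n per formulation | Factor, one arm each | Factor, pooled |
|---|---|---|---|
| One Cohort 1 group | 15 → 30 | 2.28 (1.93–2.69) | 1.79 (1.59–2.01) |
| Cohort 1, three groups pooled | 45 → 90 | 1.61 (1.46–1.77) | 1.40 (1.31–1.50) |
| Cohort 1, four groups pooled | 60 → 120 | 1.51 (1.39–1.64) | 1.34 (1.26–1.42) |
| Cohort 2 | 45 → 90 | 1.61 (1.46–1.77) | 1.40 (1.31–1.50) |

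Two Cohort 1 rows are needed because SAP 7.1 pools groups 1 to 3 (three age groups), while SAP 4.4 defines four groups of 120.

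**The case against.** **Testing at the early visits is inferred.** The eight-arm summaries are explicit, but the tests are not. The sentence on showing all time points concerns table layout and is qualified. The lists with all collection times are introduced for summary purposes. Protocol 13.1.3 speaks of selected endpoints for ANCOVA and CMH. The endpoint lists and SAP 7.8.3 are redacted, and a visit restriction could sit there. This stands as a doubt. The ANCOVA text as readable still has no visit limit, so testing at every visit remains the plain reading.

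**Eight arms have a use.** One table follows each randomised arm from baseline to the last visit, and Protocol 13.1.3 requires summaries by the combination of formulation and dose number. This stands, and it rules out replacing the eight-arm rows. Protocol 13.1.1 allows further groupings to be specified in the SAP, so an added pooled analysis fits.

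**The null is not quite exact in the per-protocol set.** That set requires all planned doses and an evaluable Day 57 or Day 140 sample, so later events help decide who is counted at Day 29. This is correct, and the four contrasts are zero by design only before that selection. It gives no reason to read them as dose effects.

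**The trial is descriptive, and the readable secondary endpoints are at Day 57 and Day 140.** This limits the weight of the point. It does not remove it, because precision is what a descriptive trial delivers.

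**Conclusion.** The point holds as a free improvement. At Day 29 (Cohort 1) and Days 56 and 84 (Cohort 2), analysis by eight arms splits identically treated children. Pooling gives about 29% narrower formulation intervals. That figure rests on equal arm sizes and not on any assumed SD; the fold factors do rest on the assumed SD. The 18.5% applies per endpoint at Day 29 if the four listed same-formulation pairs are tested there, and treats them as independent.

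A reader might infer four things that the documents do not support:
- **That the SAP orders these tests at every visit.** It orders the summaries; the tests follow only from the absence of a restriction.
- **That the 14-pair list gives four null tests in Cohort 2.** It has no 2-versus-3-dose pairs. There the problem arises through the applicable pairwise comparisons, 4 of 28.
- **That the chance of a spurious dose-number result is 56%.** Over two assays and two antigens, 1 − 0.95^16 = 56.0%, but only if all 16 tests are independent. Results from the same children are correlated, so this is a ceiling.
- **That the primary analysis is affected.** By Day 57 and Day 140 the regimens have diverged, and eight arms are then the right structure.

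**What to change.** In SAP 7.8.2, for Day 29 (Cohort 1) and Days 56 and 84 (Cohort 2):
- Add summaries and models of GMT, BT50, GMFR and seroresponse by formulation (four levels), pooling the two dose-number arms.
- Limit tests at these visits to the six formulation pairs.
- Keep the eight-arm rows that Protocol 13.1.3 requires as description only, with no dose-number tests before the regimens diverge.
- Keep the eight-arm analysis from Day 57 and Day 140 on.

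Record the change in SAP 7.13. The cost is one SAP paragraph and a four-column table shell for the early visits. It needs no new data, and because the pooled analysis is added and the required rows stay, no protocol amendment.

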#### Secondary and Exploratory Binomial Immunogenicity Endpoints

The binomial secondary and exploratory seroresponse rate endpoints are listed below:

- CCI [REDACTED]
- [REDACTED]

- CCI
- 
- 
- 
- 

Rates of seroresponse to both NoV GI.1 VLP and GII.4 VLP will be summarized and analyzed similarly to the primary immunogenicity endpoint, for both the PPS and FAS.

Seroresponse rate to each VLP (GI.1 VLP or GII.4 VLP antibody titers) will be summarized similarly to the primary immunogenicity endpoint for the PPS only.

Graphics may be prepared to present seroresponse over time and to concisely illustrate the effects of formulation and number of doses within groups.

#### Secondary and Exploratory Continuous Immunogenicity Endpoints

The secondary and exploratory continuous immunogenicity endpoints are listed below:

- CCI
- 
- 
- 
- 
- 
- 
- 

GMT, BT50 and GMFR will be summarized descriptively, as described in the General Methodology of Section 7.9, for each of the 8 formulation/dose combinations (4 formulation arms; 1 and 2 [or 2 and 3] doses), by group, at each scheduled time point. These summaries will

also be provided at the cohort level, ie, by pooling subjects across the relevant groups. These summaries will be provided for the subjects in the PPS and FAS.

The GMT and BT50 will be calculated as the anti-logarithm of  $\sum(\log \text{transformed titer}/n)$ , ie, as the anti-logarithm transformation of the mean of the log-transformed titer, where n is the number of subjects with titer information. The GSD for GMT and BT50 will be calculated as the anti-logarithm transformation of the standard deviation of the log-transformed titer. The 95% CI will be calculated as the anti-logarithm transformation of the upper and lower limits for a two-sided CI for the mean of the log-transformed titers.

[figure not shown]
GMFR will be calculated as anti-logarithm of  $\sum (\log \text{transformed (post-vaccination titer/ pre-vaccination titer)}/n)$ . The GSD and 95% CIs for GMFR will be calculated similarly to those for GMT and BT50.

GMT, BT50 and GMFR will be analyzed with an ANCOVA model examining the effect of formulation/dose combination using the log-transformed value as the dependent variable and the corresponding log-transformed baseline value as a covariate. The ANCOVA models will include group as a factor for analyses of Cohort 1 with a group by formulation/dose combination interaction term included if appropriate, as follows. If the interaction term p-value is  $\leq 0.05$ , the term will remain in the model. If the p-value is  $>0.05$  it will be removed. For Cohort 1, the model will include estimates for treatment (formulation/dose combination) effect within each group, and at the cohort level across groups. A factor for country will be included. All the applicable pairwise comparisons will be provided with lower levels as the reference groups, with no adjustments for multiplicity. The 14 comparisons of interest listed in the *General Methodology* of Section 7.8 will be tested. The analyses will be based on the PPS.

Box plots and/or reverse cumulative distribution (RCD) curves will be provided for comparisons of interest. Other graph formats may be included for illustration purposes.

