Background and Rationale: 
Noroviruses (NoV) have emerged as the single most significant cause of epidemic outbreaks of non-bacterial gastroenteritis worldwide. These outbreaks commonly result in significant morbidity and mortality in almost all age groups. Those most at risk are the elderly, the very young, and immunocompromized individuals. Noroviruses cause acute debilitating illness characterized by vomiting, diarrhea, and abdominal pain. There are no substantial differences in clinical presentation between adults and children, although children less than 1 year of age present more frequently with diarrhea and less frequently with vomiting than other age groups. The duration of the diarrhea is also longer in this age group with a median duration of 6 days compared to 1 to 3 days in other age groups [1]. In the European Union (EU), for children under 5 years of age, it is estimated that each year there are 5,600,000 cases of NoV gastroenteritis [2], resulting in 380,000 outpatient and 147,000 emergency room visits (population adjusted from Hall, 2011 [3]), 30,000 to 47,000 hospitalizations (population adjusted from Phillips, 2010 [2]) and as many as 200 deaths (assumes ratio of deaths to hospitalizations is the same as rotavirus in the pre-vaccine era). For children below the age of 5 years in high income countries, an estimated figure of 64,000 episodes of NoV disease occur requiring hospitalization [4]. Whereas mortality due to NoV disease in the pediatric population is rare in industrialized countries, it is frequent in developing countries. In developing countries, mortality from NoV disease in children below the age of 5 years is approximately 200,000 deaths per year [4, 5]. Although potentially a cause for hospitalization in infants, there are fewer deaths than expected possibly due to the protection offered by maternal antibodies during the first 6 months of life. A study in Finland found that 68% of infants less than 6 months old had immunoglobulin G (IgG) antibodies against GII.4 NoV with high avidity, which likely reflects acquired maternal IgG antibodies (from transplacental transfer), compared to the antibodies found in infants aged 7 to 12 months. However, the presence of immunoglobulin A (IgA) antibodies in 20% of these children suggests that maternal antibodies do not offer full protection [6]. Vaccination of young infants with a NoV vaccine during the first 6 months of life may provide protection thereafter, when infants and young children are at highest risk of acquiring NoV disease.
 
In addition to the inherent morbidity and mortality problem, NoV infections exact a significant socioeconomic toll on businesses, hospitals, schools, and other closed settings dealing with outbreaks [7]. As the burden of rotavirus in children decreases through the childhood rotavirus vaccination programs, NoV infections and disease are likely to increase with consequences extending beyond this population [8]. A prophylactic approach could counter this.
 
The vaccine in this trial is based on NoV virus-like particles (VLPs) as the antigens. Norovirus VLPs are non-infectious because they do not contain viral genomic ribonucleic acid (RNA) and are immunogenic because they preserve particulate antigen conformation and structure that mimic functional interactions of the virus with cellular receptors. The vaccine also contains the single Al(OH)3 adjuvant.
 
Aluminum hydroxide [Al(OH)3] has been shown to enhance the antigenicity and immunogenicity of vaccines. The rationale for an Al(OH)3 adjuvanted intramuscular (IM) NoV VLP vaccine is based on the low immune responses previously observed in healthy adults after oral administration of Norwalk Virus VLP vaccine [9, 10, 11]. Aluminum adjuvant has a demonstrated safety profile of over 6 decades [12]). The aluminum concentration per dose was selected
		

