#### **7.4 Demographic and Baseline Characteristics**

Age, gender, race, and other baseline characteristics will be summarized descriptively by formulation arm and dose group, overall and separately for each of the groups in the cohorts, for randomized subjects and subjects in the PPS. Baseline characteristics will include the numbers and percentages of subjects with Baseline (pre-vaccination) values of antibody titers below the LLoQ for each assay (Pan-Ig, HBGA, and IgA) for each VLP antigen (GI.1 and GII.4). In addition the number and percentage of subjects with values below the LLoQ for all assays and antigens will be provided.

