### 7.8.1 Primary Immunogenicity Endpoint(s)

The primary immunogenicity endpoint for this trial is seroresponse rate, defined as the percentage of subjects with a 4-fold rise or greater, in serum anti-NoV antibody titers for both GI.1 VLP and GII.4 VLP as measured by Pan-Ig ELISA at Day 57 (Cohort 1) and Day 140 (Cohort 2). The primary analyses will be based on the PPS data but will also be provided using the FAS.

The seroresponse rates and 95% CIs will be summarized (as described in the General Methodology of Section 7.9) for each of the 8 formulation/dose combinations (4 formulation arms; 1 and 2 [or 2 and 3] doses), by group. These summaries will also be provided at the cohort level (pooling subjects across groups in Cohort 1). The 95% CI of seroresponse rate will be

calculated using the exact (Clopper-Pearson) method. These summaries will be provided for the subjects in the PPS and FAS.

Statistical analyses of the primary endpoint will be performed at the cohort level using the CMH method stratified by group to assess the effect of formulation/dose schedule. Common risk differences and corresponding 95% CIs will be provided for all pairwise comparisons of interest, without adjustments for multiplicity. The 14 comparisons of interest (listed in the *General Methodology* of Section 7.8 above) will be tested.

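### No visible primary or secondary immunogenicity model uses age within group; adding it, above all for Group 4, could gain precision at almost no cost

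*SAP*

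**What the plan says.** **Continuous endpoints.** SAP 7.8.2 says "GMT, BT50 and GMFR will be analyzed with an ANCOVA model examining the effect of formulation/dose combination using the log-transformed value as the dependent variable", with the "corresponding log-transformed baseline value as a covariate". It adds: "The ANCOVA models will include group as a factor for analyses of Cohort 1". SAP 7.8 (General Methodology) adds: "A factor for country will be included in all models".

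**Seroresponse.** SAP 7.8.1: "Statistical analyses of the primary endpoint will be performed at the cohort level using the CMH method stratified by group". General Methodology limits that stratification to Cohort 1. No baseline titre enters.

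**Age.** Protocol 9.1.2 collects age as demographic data. SAP 7.4 gives its only stated use: "Age, gender, race, and other baseline characteristics will be summarized descriptively by formulation arm and dose group". Protocol 8.3 stratifies randomisation by country and group, with no age bands inside a group. Protocol 13.1.3 once speaks of stratifying other dichotomous endpoints by age, but refers back to the method already described, which stratifies by group.

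**Background.** The Protocol Trial Summary says that infants have fewer norovirus deaths than expected, "possibly due to the protection offered by maternal antibodies during the first 6 months of life". It also reports that 68% of infants under 6 months in one study had IgG against GII.4, likely maternal, and compares them with infants aged 7 to 12 months.

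**The concern.** For Group 4 the terms reduce to arm, log baseline titre and country in the ANCOVA, and to arm alone in the primary CMH analysis. Yet the group spans the months in which the protocol itself describes maternally derived antibody. If response varies with age inside the group, that variation stays in the residual and widens the intervals used to compare formulations. The trial has no immunogenicity power calculation and about 45 children per arm in Group 4, so precision that costs no extra children is worth having.

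The gap is clearest for the primary endpoint. The ANCOVA at least holds baseline titre. The CMH analysis does not, although a 4-fold rise is defined relative to baseline.

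**Working it through.** **1. Inputs from the documents.** Group 4 has 360 children in 8 equal arms: 360/8 = 45. Each Cohort 1 group has 120/8 = 15 per arm. The only design calculation is Table 13-a, the probability of at least one adverse event, 1 − (1 − p)^N. It reproduces: p = 0.33%, N = 480 gives 79.5%; p = 2%, N = 120 gives 91.1%. It says nothing about immunogenicity precision.

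**2. Assumed inputs.** The documents give no SD of log titre, no correlation of age with response and no distribution of enrolment age. I take log10 SD = 0.5, uniform ages within each group, and ρ = 0.1, 0.3 or 0.5, where ρ is the partial correlation of age with log titre given the existing terms.

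**3. Gain in the ANCOVA (Group 4).** Residual variance is multiplied by 1 − ρ², interval width by √(1 − ρ²), and effective size is 45/(1 − ρ²). The interval factor for a pairwise GMT ratio is 10^(1.96 × 0.5 × √(1 − ρ²) × √(2/45)).

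| ρ | width change | effective n per arm | 95% interval, ×/÷ |
|---|---|---|---|
| 0 | none | 45 | 1.61 |
| 0.1 | −0.5% | 45.5 | 1.605 |
| 0.3 | −4.6% | 49.5 | 1.57 |
| 0.5 | −13.4% | 60 | 1.51 |

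With SD from 0.4 to 0.7, the factor without age runs from 1.46 to 1.95. The percentage changes do not depend on the SD.

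**4. How much baseline titre may already absorb.** Partial correlation = (r_ay − r_by·r_ab)/√[(1 − r_by²)(1 − r_ab²)], where a is age, y is response and b is baseline. Take r_ay = 0.3 and r_ab = −0.6:
- r_by = −0.3: (0.30 − 0.18)/√(0.91 × 0.64) = 0.16.
- r_by = −0.5: (0.30 − 0.30)/√(0.75 × 0.64) = 0.
- r_by = 0: 0.30/√(1 × 0.64) = 0.375.

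So adjusting for baseline can remove the age gain or leave it intact.

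**5. Chance age imbalance.** The SE of a two-arm difference in mean age is SD × √(2/n). Group 4, uniform over 6 to 26 weeks: SD = 20/√12 = 5.77 weeks; SE = 5.77 × √(2/45) = 1.22 weeks; 95% range ±2.4 weeks. With 15 per arm, the same formula gives ±1.03 years in Group 1, ±0.62 years in Groups 2 and 2a, and ±1.2 months in Group 3. A Group 4 imbalance at its 95% limit moves a GMT ratio by 10^(ρ × 0.5 × 1.96 × √(2/45)) = 1.05, 1.15 or 1.27-fold for ρ = 0.1, 0.3 or 0.5.

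**6. Are intervals without age still valid?** A simulation of 3,000 trials (8 arms of 45, uniform ages, log10 SD 0.5, arm with or without age, no other covariates) gave coverage without age of 94.8%, 94.7% and 94.5% at ρ = 0, 0.3 and 0.5. The mean log10 half-width fell from 0.207 to 0.198 at ρ = 0.3 and from 0.207 to 0.180 at ρ = 0.5. At ρ = 0 it stayed at 0.207, so a useless age term costs almost nothing.

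**7. Seroresponse.** The width formula in step 3 does not carry over to a risk difference. I give no figure there.

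**The case against.** The case against is that the plan contains no error. Randomisation is stratified by country and group, the ANCOVA already adjusts for a strong candidate covariate, and the trial is declared descriptive with no precision target to miss. That stands. Three stronger readings are tempting, and the documents do not support them.

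- **A reader might infer that age imbalance biases the arm contrasts.** Under randomisation the contrasts are unbiased, and the ordinary interval already allows for chance imbalance (step 6). The shifts in step 5 are part of that sampling error. The per-protocol set does exclude children after randomisation, but nothing in the documents ties those exclusions to age by arm.
- **A reader might infer that age is a leading predictor of response to this vaccine.** The documents do not say so. They describe antibody prevalence in young infants and offer maternal protection only as a possibility. Baseline titre measures that antibody directly, so the ANCOVA may already hold most of the effect. This reply does not reach the primary CMH analysis, which uses no baseline titre.
- **A reader might infer that no immunogenicity model at all uses age.** SAP 7.8.3 and the exploratory endpoint lists are redacted, so only the visible primary and secondary models can be checked.

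Two limits on size also stand. Spacing from routine vaccines could bunch enrolment ages in Group 4 and shrink the imbalance. Cohort 1 primary comparisons are made at cohort level, about 4 × 15 = 60 per arm if all four groups are pooled, with group removing between-group age differences.

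**Conclusion.** The point holds as an inexpensive improvement and not as a flaw that threatens any conclusion. In the visible primary and secondary analyses, age within group is unused. For Group 4 the primary analysis uses no baseline information at all. The loss is one of precision. In the Group 4 ANCOVA it ranges from negligible (0.5% of interval width at ρ = 0.1) through modest (about 5% at 0.3) to useful (about 13% at 0.5). It may be near zero if baseline titre carries the age effect. These figures rest on assumed correlations, and the age-imbalance figures on uniform enrolment ages; neither can be taken from the documents. The gain for seroresponse is not quantified, but the argument is stronger there because neither age nor baseline titre is used.

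**What to change.** Before unblinding of the groups concerned:

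1. Add age at first vaccination, continuous and centred within group, to the ANCOVAs in SAP 7.8 and 7.8.2. In Cohort 1, state whether each group has its own slope.
2. For the primary seroresponse endpoint (SAP 7.8.1), report a standardised risk difference from a model with arm, age, log baseline titre and, in Cohort 1, group. The title of SAP reference 2, cited for the CMH method, already names covariate-adjusted differences in proportions by logistic regression. Keep the planned CMH result beside it, and as the fallback if the logistic model cannot be fitted because an arm's seroresponse is near 0% or 100%.
3. For Groups 1 and 2, label the age-adjusted results a sensitivity analysis. SAP 7.12 lets aggregate unblinded interim results reach limited sponsor personnel, and these two groups report first, so a covariate added now could look data-driven.

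Cost: 1 degree of freedom in Cohort 2, up to 4 in Cohort 1, and the assumption that the age effect is linear within group. No new data are needed.
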